1.5 Overview of Proposed Study

UC-961 will be examined for safety and tolerability in patients who enrolled and completed UC-961 infusions on the phase 1 first-in-man clinical trial without dose limiting toxicity at doses at or below the RP2D, and receive retreatment with UC-961 at the established biologically active dose or MTD. The primary endpoint of this phase I trial will be assessment of adverse events during continued treatment. In addition there will be assessment of clinical activity according to iwCLL working group criteria and progression free survival. Additionally, pharmacokinetic parameters will be assessed and blood samples will be collected for correlative analysis.

2.1 Primary Objective:

2.1.1 To determine the safety and tolerability of UC-961 when administered for an extended duration.

2.2 Secondary Objectives:

- 2.2.1 To determine the clinical activity of biweekly doses of UC-961, including overall response rate (2008 iwCLL guidelines) and progression free and overall survival (new clinical endpoint from the initial phase 1 trial).
- 2.2.2 To assess the SD, PR, and MRD- rates

2.3 Exploratory Objectives:

2.3.1 To assess the mechanism of action through immunophenotypic (FACS, ELISA), nanoproteomic ROR1 signaling pathway analysis and pharmacodynamic studies including ROR1⁺ cancer stem cell cycle and self-renewal assays.

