2.4 Primary Endpoint

2.4.1 Safety and tolerability with extended dosing of UC-961 based on ongoing evaluation of AEs during treatment and 3 month follow up

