4.0 INVESTIGATIONAL TREATMENT PLAN

4.1 Dose Assignment

The dose of UC-961 is currently undergoing evaluation in a phase 1 study.

During the extension treatments, patients will be assigned to receive the highest safe dose from an ongoing phase 1 study, or the established maximum tolerated dose/ recommended phase 2 dose (which may increase as the phase 1 trial accrues additional patients). Patients will receive the same dose of UC-961 for 1 course, which consists of 8 doses (every 14 days for 4 doses, then every 28 days for 4 doses). As of April 2016, the highest safe dose is 8 mg/kg.

Following 1 course, patients will be assessed for response, and then are eligible to receive a second course. Patients with a complete response or partial response will continue at the same

dose. Patients with stable disease or progressive disease will receive a higher dose of UC-961, if a higher safe dose has been established in the concurrent CLL Phase 1 trial by that time.

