4.2 Dose Limiting Toxicity

Dose-Limiting Toxicity (DLT) is defined as any of the following adverse events that are considered by the investigator to be possibly, probably, or definitely related to the study agent UC-961 within the 28 days of the start investigational treatment:

- CTCAE Grade 3 or higher non-hematologic toxicity, except for: Grade 3 infections lasting < 7 days that have resolved, or one occurrence of Grade 3 infusion reaction; or
- Grade 4 or higher hematologic toxicity (by modified iwCLL criteria); or
- Any AE requiring a dose delay of greater than 28 days;

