4.5 Criteria for dosing

Doses are administered on day 1, 15, 29, 43, 57, 85, 113, and 141 (+/-3 days) if the patient is without ongoing Grade 3 non-hematologic or Grade 4 hematologic toxicities attributable to UC-961.

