10.0 STATISTICAL CONSIDERATIONS

The primary aim of the study is to determine the safety of UC-961 therapy given at the currently used, biologically active dose, or RP2D for an extended duration.

Safety will be assessed through summaries of adverse events, clinical laboratory abnormalities, and changes in physical exam and vital signs. All subjects who receive a single dose of study medication will be considered evaluable for safety.

Adverse events will be listed, documenting the course, outcome, severity, and relationship to the study treatment. Incidence rates of AEs and the proportion of subjects prematurely withdrawn from the study due to AEs will be shown.

The primary endpoint of this study is the rate of dose-limiting toxicity (DLT).

SECONDARY ANALYSIS

Secondary Endpoints are overall response rate by IWCLL criteria following 6 months of biweekly dosing of UC-961 (Hallek *et al.*, 2008); Progression free and overall survival (progression determined by IWCLL working group criteria); and SD, PR, and MRD-rates, as well as individual components of response (reduction in leukemia count, reduction in adenopathy and splenomegaly, and improvement in BM function), as determined by IWCLL working group criteria.

These secondary endpoints will be summarized by dose cohort, clinical characteristics and overall using percentages, means and median survival estimates as appropriate. Data will also be presented graphically with Kaplan Meier plots, box plots, and bar charts. All statistics will be presented with 95% confidence intervals. The analysis will be descriptive; thus no correction for multiple analyses will be made and no formal tests of hypothesis will be done.

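### Section 10 makes the 28-day DLT rate the primary endpoint, but Sections 1.5 and 2.4.1 and the synopsis name adverse events over extended treatment; the DLT rate cannot answer the extended-duration safety aim

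*Combined protocol and SAP*

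**What the plan says.** The primary endpoint is stated in four places, and they do not agree.

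- **Section 10.0:** the aim is safety at the current dose, "biologically active dose, or RP2D for an extended duration". The same section then says: "The primary endpoint of this study is the rate of dose-limiting toxicity (DLT".
- **Section 2.4.1**, repeated in the synopsis: "Safety and tolerability with extended dosing of UC-961 based on ongoing evaluation of AEs during treatment and 3 month follow up".
- **Section 1.5:** "The primary endpoint of this phase I trial will be assessment of adverse events during continued treatment", with no mention of the 3-month follow-up.

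The DLT rate is not listed as an endpoint in the synopsis or in Sections 2.4 to 2.6. Section 4.2 limits a DLT to qualifying events judged at least possibly "related to the study agent UC-961 within the 28 days of the start investigational treatment".

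Section 10 also plans summaries of adverse events, laboratory abnormalities, physical examination and vital signs in everyone who receives a dose: "Incidence rates of AEs and the proportion of subjects prematurely withdrawn from the study due to AEs will be shown". These carry no 28-day limit, but they are not called the primary endpoint.

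**The concern.** The study exists to learn what happens when dosing is prolonged. Patients enter after four infusions in the phase 1 trial, tolerated without a DLT (synopsis schema). On the nominal schedule the 28-day window then covers two infusions, fewer than they have already tolerated.

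A rate confined to that window cannot include toxicity that appears later. This covers anything that follows a Course 2 dose increase, which Section 4.1 provides for: "Patients with stable disease or progressive disease will receive a higher dose of UC-961, if a higher safe dose has been established". It also leaves out events judged unrelated and most lower-grade events.

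With two definitions in force, it is open which result will be reported as the primary one. The analysis is descriptive, with no hypothesis test, so the endpoint definition is the main safeguard against making that choice after the data are seen.

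**Working it through.** The plan gives no target DLT rate, power or event rate, so there is no figure of its own to reproduce. Steps 1 and 2 use the schedule; step 2 adds one assumption about follow-up. Step 3 is illustration only.

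**1. Infusions inside the window.** Section 4.5 gives the Course 1 schedule: "Doses are administered on day 1, 15, 29, 43, 57, 85, 113, and 141 (+/-3 days". Section 5.4 puts Course 2 on Days 197 to 337, and Section 1.4 allows 16 infusions in all.

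- Nominal schedule: Days 1 and 15 fall inside 28 days. That is 2/8 = 25% of Course 1 and 2/16 = 12.5% overall.
- If the third infusion is given on Days 26 to 28, or Day 29 is counted: 3/8 = 37.5% and 3/16 = 18.8%.
- Course 2: none. Nothing in Section 4.2 reopens the window.

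**2. Calendar time inside the window.** The documents do not say what the 3-month follow-up is counted from. Assume 90 days after the last dose.

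- One course: 141 + 90 = 231 days; 28/231 = 12.1%.
- Two courses: 337 + 90 = 427 days; 28/427 = 6.6%.
- Without follow-up, to the response assessments on Days 169 and 365: 28/169 = 16.6% and 28/365 = 7.7%.

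**3. Illustration.** Assume a risk p = 20% per patient of a related, DLT-grade event over the full period, and that all 33 anticipated patients complete. Then 33 × 0.20 = 6.6 affected patients are expected. Let q be the probability of an event inside the window. Expected DLTs are 33q, and the chance of observing none is (1 − q)^33.

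- (a) Constant calendar hazard: q = 1 − (1 − p)^(28/T), T = 231 or 427.
- (b), (c) Constant risk per infusion: q = 1 − (1 − p)^(k/K), k = 2 or 3, K = 8 or 16.
- (d) Half the cumulative hazard in the first 28 days: q = 1 − (1 − p)^0.5.

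| Scenario (one course / two courses) | q | Expected DLTs | Chance of 0/33 |
|---|---|---|---|
| (a) calendar hazard | 2.7% / 1.5% | 0.9 / 0.5 | 41% / 62% |
| (b) per infusion, k = 2 | 5.4% / 2.8% | 1.8 / 0.9 | 16% / 40% |
| (c) per infusion, k = 3 | 8.0% / 4.1% | 2.7 / 1.4 | 6% / 25% |
| (d) front-loaded | 10.6% | 3.5 | 2.5% |

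For (b), the chance of 0/33 is 42% / 65% at p = 10% and 5% / 23% at p = 30%. An observed 0/33 has an exact 95% interval of 0 to 10.6%, and that interval speaks only to the first 28 days.

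**The case against.** The strongest reply is that the label drives nothing. No sample size, threshold or test rests on the DLT rate. The stopping rules in Section 4.9 use deaths and related Grade 4 non-hematologic events, with no 28-day limit. The DSMB sees all adverse events every six months (Section 11.4). Section 10 tabulates adverse events in all dosed patients. All of this is true, and it means that long-term safety data are not missing. It does not settle which result is primary.

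The illustration can also be attacked, and much of that stands.

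- The 20% risk has no source in the documents. The phase 1 adverse event table shows only Grades 1 and 2.
- Scenario (d) fixes its share at half by construction. With 80% or 90% of the cumulative hazard in the first 28 days, the same formula gives 16.3% or 18.2% against 20%.
- Scenario (a) keeps the hazard constant through the assumed 90 days off drug, which lowers the share in the window.
- The two-course figures assume that everyone receives 16 infusions, so they are extremes.

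The table therefore shows how strongly the answer depends on when toxicity occurs. It is not an estimate of what will be missed.

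Finally, Section 4.7 uses the term DLT loosely for Grade 4 toxicity without mentioning a window. That does not override the definition in Section 4.2.

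**Conclusion.** The concern holds and must be fixed. Section 10 contradicts Sections 1.5 and 2.4.1 and the synopsis on the primary endpoint, and the endpoint it names does not match its own stated aim. This conclusion comes from the text and needs no event rate.

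The size that rests on the documents is 2 of 8 Course 1 infusions and 2 of up to 16 overall (3 of each with an early or counted Day 29 infusion), and none from Course 2. The calendar shares of 12% and 7% also rest on the 90-day assumption. The chances of seeing no DLT, 2.5% to 62% at an assumed 20% risk, rest on the assumed risk, hazard shape and full completion.

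The defect is limited to what is labelled primary. Toxicity after Day 28 will be reported descriptively under the existing plan.

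**What to change.** **In Section 10**, replace the DLT sentence with the Section 2.4.1 endpoint: adverse events from first dose through treatment and the 3-month follow-up, in all patients given at least one dose. Report patient-level incidence with exact 95% confidence intervals, and specify the grade and attribution categories to be tabulated so that the headline result is defined in advance. Related events meeting the Section 4.2 criteria at any time in that period can be one named component. Its dose-delay criterion can apply only while dosing continues. Keep the 28-day DLT rate as a supportive summary.

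**For consistency**, state what the 3-month follow-up is counted from and add it to Section 1.5. Report how many patients were still under adverse event follow-up at 3 months and why it ended for the others, since Section 4.10 lets follow-up stop when subsequent therapy begins.

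Leave the treatment rules that use the DLT definition unchanged.

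**Cost:** wording in Sections 10 and 1.5 and a few more tables. No visits are added, because adverse events are already assessed at infusions, response assessments and follow-up visits. Three-month ascertainment is not assured for patients who start other therapy, and the headline rate may look less favourable than a 28-day DLT rate.

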11.0 STUDY MANAGEMENT

11.1 Conflict of Interest

Any investigator who has a conflict of interest with this study (patent ownership, royalties, or financial gain greater than the minimum allowable by their institution, etc.) must have the conflict reviewed according to UCSD conflict of interest policy.

11.2 Institutional Review Board (IRB) Approval and Consent

The IRB should approve the consent form and protocol prior to any study-related activities. It is expected that the IRB will have the proper representation and function in accordance with federally mandated regulations.

In obtaining and documenting informed consent, the investigator should comply with the applicable regulatory requirement(s), and should adhere to Good Clinical Practice (GCP) and to ethical principles that have their origin in the Declaration of Helsinki.

Before recruitment and enrollment onto this study, the patient will be given a full explanation of the study and will be given the opportunity to review the consent form. Each consent form must include all the relevant elements currently required by the FDA Regulations and local or state regulations. Once this essential information has been provided to the patient and the investigator is assured that the patient understands the implications of participating in the study, the patient will be asked to give consent to participate in the study by signing an IRB-approved consent form.

Prior to a patient's participation in the trial, the written informed consent form should be signed and personally dated by the patient and by the person who conducted the informed consent discussion.

11.3 Subject Data Protection

In accordance with the Health Information Portability and Accountability Act (HIPAA), subjects who have provided written informed consent must also sign a subject authorization to release medical information to the study Sponsor and allow a regulatory authority, or Institutional Review Board access to subject's medical information relevant to the study.

11.4 Data and Safety Monitoring

In addition to adverse event monitoring and clinical oversight by the principal investigator and co-investigators, quality assurance of the study will be performed by the clinical trials office internal monitor.

This study will also use the UCSD Moores Cancer Center Data Safety and Monitoring Board (DSMB) to provide oversight in the event that this treatment approach leads to unforeseen toxicities. Data from this study will be reported after every 6 months, or sooner if required for clinical study stopping rules (Section 4.9), and will include:

- 1) the protocol title, IRB protocol number, and the activation date of the study.
- 2) the number of patients enrolled to date
- 3) the date of first and most recent patient enrollment
- 4) a summary of all adverse events regardless of grade and attribution
- 5) a response evaluation for evaluable patients when available
- a summary of any recent literature that may affect the ethics of the study.

11.5 Record Retention

Study documentation includes all Case Report Forms, data correction forms or queries, source documents, Sponsor-Investigator correspondence, monitoring logs/letters, and regulatory documents (e.g., protocol and amendments, IRB correspondence and approval, signed patient consent forms).

Source documents include all recordings of observations or notations of clinical activities and all reports and records necessary for the evaluation and reconstruction of the clinical research study.

Government agency regulations and directives require that the study investigator must retain all study documentation pertaining to the conduct of a clinical trial. In the case of a study with a drug seeking regulatory approval and marketing, these documents shall be retained for at least two years after the last approval of marketing application in an International Conference on Harmonization (ICH) region. In all other cases, study documents should be kept on file until three years after the completion and final study report of this investigational study.

11.6 Obligations of Investigators

The Principal Investigator is responsible for the conduct of the clinical trial at the site in accordance with Title 21 of the Code of Federal Regulations and/or the Declaration of Helsinki. The Principal Investigator is responsible for personally overseeing the treatment of all study patients. The Principal Investigator must assure that all study site personnel, including sub-investigators and other study staff members, adhere to the study protocol and all FDA/GCP/NCI regulations and guidelines regarding clinical trials both during and after study completion.

The Principal Investigator at each institution or site will be responsible for assuring that all the required data will be collected and entered onto the Case Report Forms. Periodically, monitoring visits will be conducted and the Principal Investigator will provide access to his/her original records to permit verification of proper entry of data. At the completion of the study, all case report forms will be reviewed by the Principal Investigator and will require his/her final signature to verify the accuracy of the data.

13.0 APPENDICES

Appendix A. Performance Status

PERFORMANCE STATUS CRITERIA ECOG Performance Status		
Score	Description	
0	Fully active, able to carry on all pre-disease performance without restriction	
1	Restricted in physically strenuous activity but ambulatory and able to carry out work of a light or sedentary nature, e.g., light house work, office work	
2	Ambulatory and capable of all self-care but unable to carry out any work activities. Up and about more than 50% of waking hours	
3	Capable of only limited self-care, confined to bed or chair more than 50% of waking hours	
4	Completely disabled. Cannot carry on any self-care. Totally confined to bed or chair	
5	Dead
